5.1 Eligibility

5.1.1 Inclusion Criteria

All adult (age ≥ 18 years) patients admitted acutely to one of the participating ICUs during the 14-day inception period.

² amisulprid (N05AL05), aripiprazol (N05AX12), asenapin (N05AH05), clozapin (N05AH02), lurasidon (N05AE05), olanzapin (N05AH03), paliperidon (N05AX13), quetiapin (N05AH04), risperidon (N05AX08), sertindol (N05AE03), ziprasidon (N05AE04).

5.1.2 Exclusion Criteria

- Pre-diagnosed mental illness of schizophrenia and/or psychosis and/or major depression (ICD 10; F20-29; F30, F31, F32, F33)
- Terminal status (i.e., expected to survive < 24 hr. and/or withdrawal of life-support)
- Pre-diagnosed neurodegenerative disorders Dementia and Parkinson (ICD 10; F02-04)
- Mental illness recurring institutionalization or acquired or congenital mental retardation
- Patients with congenital or acquired brain damage, i.e.; stroke in the past 2 weeks, transient cerebral ischemic in the past 2 weeks, subarachnoid haemorrhage, cerebral cancer, meningitis, encephalopathies, ongoing seizures and suspected anoxic brain injury or traumatic brain injury
- Patients admitted with hepatic coma, drug overdose or suicide attempt (within the past 6 months necessitating hospitalization)
- Blind and/or deaf

5.2 Readmission to an ICU

When included patients in the 14-day inception period are discharged from the ICU and, are readmitted during the same hospital admission, to an ICU that participates in AID-ICU registration will be continued. If the included patient is discharged from the hospital and readmitted at another ICU at another hospital he/she will not have data registered from that ICU.

5.3 Patients transferred between hospitals

Patients transferred from one ICU participating in AID-ICU to another ICU participating in AID-ICU: day from registration will be continued at the receiving hospital and the investigator at the last hospital will complete follow-up.

Patients transferred from an ICU participating in AID-ICU to an ICU not participating in AID-ICU: Collection of data will end at discharge from AID-ICU participating ward except for the time dependent outcome measures.

5.4 Patients eligible for RBANS assessment (only in Denmark)

We will chose a convenience sample of patients who have been admitted to a Danish ICU and who are alive at 6 months with no new diagnosis of mental illness such as schizophrenia and/or psychosis and/or major depression (ICD 10; F20-29; F30, F31, F32, F33), no new neurodegenerative disorders Dementia and Parkinson (ICD 10; F02-04), no stroke in the past 2 weeks before the test, no suspected anoxic brain injury or acute traumatic brain injury, blind and/or deaf after admission or have poor Danish and English skills. The patients for RBANS assessment will be sampled based on pragmatic selection (availability of patient and staff).

5.5 Study completion

When the 14-day inception period and the 90-day (for some sites 6 month) follow-up period has ended.

6. Clinical and laboratory assessments – Methodology

See appendix 1.

6.1 Patient evaluation

Baseline patient characteristics

1. Age on the day of ICU admission (years)

2. Gender (male/female)
3. Simplified Acute Physiology Score II (SAPS II) within the first 24 hours of the ICU admission (0-163 points)
4. Use of dialysis, vasopressors or inotropes (noradrenaline (C01CA03), adrenaline (C01CA24), dobutamine (C01CA07), dopamine (C01CA04), milrinone (C01CE02), levosimendan (C01CX08) vasopressin (H01BA01) or phenylephrine (C01C A06) and/or medical ventilation (y/n)
5. Days admitted in the hospital prior to ICU admission (number of days)
6. Type of admission diagnose (sepsis y/n, trauma y/n, surgery 24 hour prior to admission y/n, elective surgery y/n, emergency surgery y/n)
7. Treatment with antipsychotics (N05A), anti-Parkinson (N04), antidepressant (N06A) and benzodiazepine (N05BA) prior to hospital/ICU admission
8. Risk factor status prior to hospital/ICU (*Previous delirious episodes defined as: patients receiving one or more doses of haloperidol, AND described as delirious (documented CAM-ICU positive or ICDSC ≥ 4 point (0-8 point) or DOS >3 point (0-13/day point), ICD-10 code (DF05, DF050, DF058), or agitated and/or not cooperative and/or eyes open and big with no contact (Glasgow Coma Score (GCS) > 7) and/or anxiety, or restrained to the bed), smoking more than 10 cigarettes a day yes/no, alcohol abuse more than 3 units (1 units defined as 12 g of alcohol) a day yes/no)*)
9. Hearing or vision impairment (y/n)

Daily data collection from admission through last day of follow-up (discharge from ICU or day 90

10. Sedation assessment (the sites will only register the score (a, b or c) they use in clinical practice), as described in patient files, one score equals one positive day with sedative induced coma.
 - a. RASS score -3- (-5) (y/n) at any time during the day or
 - b. Ramsey sedations score 4-6 points (y/n) at any time during the day or
 - c. MASS score 1-0 (y/n) at any time during the day
11. Coma assessment, as Glasgow Coma Scale (GCS) score without any sedation
 - a. GCS < 8 point (y/n) at any time during the day
12. Delirium assessment (the sites will only register the score (a, b or c) they use in clinical practice), as described in patient files, one positive score equals one delirium day. (appendix 2)
 - a. CAM-ICU (positive /negative/UTA, Unable To Assess)
 - b. ICDSC ≥ 4 point (0-8 point)
 - c. DOS >3 point (0-13 point)
 - d. ICD 10 code DF05, DF050, DF058
13. Subtype description of delirium (hypo, hyper or mixed¹⁴)
14. Restrained to the bed (y/n)
15. Treatment with continuous vasopressor or inotropes at any time during this day (noradrenaline (C01CA03), adrenaline (C01CA24), dobutamine (C01CA07), dopamine (C01CA04), milrinone (C01CE02), levosimendan (C01CX08), phenylephrine (C01C A06) or vasopressin (H01BA01))
16. Use of invasive mechanical ventilation (y/n) or use of non-invasive ventilation at any time during this day (y/n)
17. Is the patient sedated at any time during this day (y/n), with continuous infusion of
 - a. Propofol (N01AX10)
 - b. Midazolam (N05CD08)
 - c. Dexmedetomidine (N05CM18) (continues > 18 hours pr./day or continuous > 4 hours between 10 pm – 06 am)
 - d. Other

18. Pain management with intravenous opioid infusion for more than 2 consecutive hours at any time during this day (y/n).
 - a. Remifentanyl (N01AH06)
 - b. Sufentanyl (N01AH03)
 - c. Fentanyl (N01AH01)
 - d. Morphine (N02AA01)
19. Pharmacologic intervention for delirium (first initial dose will be recorded, then the 24 hour accumulated verified administrated dose. Is treatment prescribed as fixed or per need or both)
 - a. Antipsychotics
 - i. Haloperidol (N05AD01) (mg/day) (prophylaxis y/n)(regular dosing mg/day or as needed mg/day)
 - ii. Olanzapine (N05AH03) (mg/day) (prophylaxis y/n)(regular dosing mg/day or as needed mg/day)
 - iii. Quetiapin (N05AH04) (mg/day) (prophylaxis y/n)(regular dosing mg/day or as needed mg/day)
 - b. Anxiolytics
 - i. Benzodiazepine (N05BA) (y/n)
 - ii. Rivastigmin (N06DA03) (y/n)
 - iii. Other (y/n)
 - c. Hypnotics and sleeping pills (y/n) if any of the below.
 - i. Zopiclon (N05CF01)
 - ii. Zolpidem (N05CF02)
 - iii. Triazolam (N05CD05)
 - iv. Lormetazepam (N05CD06)
 - v. Nitrazepam (N05CD02)
 - vi. Chloralhydrate (N05CC01)
 - vii. Melatonin (N05CH01)
 - viii. Promethazine (R06AD02)
 - ix. Other

Day 90 after ICU admission

20. Vital status (dead/alive) (if relevant, date of death)
21. Discharged from ICU (Y/N and date)
22. Discharge from hospital (Y/N and date)

6 month after ICU admission

23. Cognitive impairment assessment with RBANS (40 to 160 points)

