2.1 Background information

The American Clinical Practice Guideline for Adult Intensive Care Unit (ICU) patients in 2002 recommended haloperidol as the therapeutic agent for delirium in critically ill patients, with the requirement of monitoring side effects such as prolongation of QT intervals and arrhythmias¹. However, in the 2013 update of the guidelines this recommendation was changed; haloperidol was no longer recommended for delirium in critically ill patients due to lack of evidence of effect. The same guideline suggests that atypical antipsychotics and continuous IV infusion of dexmedetomidine rather than benzodiazepines is suggested to reduce the duration of delirium in ICU patients with delirium even though these interventions also have low level of evidence. Presently, there are no pharmacologic agents with solid evidence of effect for the treatment of delirium in ICU patients².

Delirium is a complex acute or sub-acute organic mental syndrome characterized by altered level of consciousness, comprehensive cognitive impairment, disorientation, perceptual disturbances, attention impairment, reduced or activated motor activity, disturbed sleep patterns and fluctuating motor and mental performances³. Observed incidence rates of delirium in ICU patients range from 16% to 89%⁴. According to The American Society of Critical Care Medicine the most valid and reliable monitoring tools for routine assessment of delirium is the Confusion Assessment Method for the Intensive Care Unit (CAM-ICU) and Intensive Care Delirium Screening Checklist (ICDSC)².

The risk factors for delirium can be divided into two groups: *non-correctable factors* such as previous delirious episodes, age, dementia, smoking, alcohol and other drug abuse and potentially *correctable factors* such as several categories of medication, acute severe illness, lack of sleep, uneasy environment, and co-morbidities².

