4.3 Primary and secondary outcome measures

4.3.1 Primary

Number of ICU patients with delirium intervened with haloperidol (N05AD01)

(Definition: Patients receiving one or more doses of haloperidol and are described as delirious. Delirium defined as below in secondary outcome 2).

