4.3.2 Secondary

1. Number of ICU patients with delirium intervened with other antipsychotics than haloperidol
(Definition: Patients receiving one or more doses of 2nd generation anti-psychotics² including olanzapin (N05AH03), rivastigmin (N06DA03), risperidon (N05AX08) and quetiapine (N05AH04),

¹ Denmark, Norway, Sweden, Finland, Netherland, Switzerland, Germany, United Kingdom, Belgium, Spain, Italy, Canada, Brazil and France

AND described as delirious (see definition in secondary outcome 2. Number of patient with delirium)

2. Number of patients with delirium

(Definitions: ICU documented CAM-ICU positive or ICDSC ≥ 4 points (0-8 points) or DOS >3 points (0-13/day points), ICD-10 code (DF05, DF050, DF05), or agitated and/or non-cooperative and/or eyes open wide with no contact (Glasgow Coma Score (GCS) > 7) or restrained to the bed).

3. Mortality at 90 days

(Definition: Death within 90 days of ICU admission)

4. Days alive in ICU without coma and/or delirium

(Definition Coma: Number of calendar days the patient is alive without coma in the period from ICU admission to discharge. Coma defined as RASS (Richmond Agitation Sedation Score) score -3 to -5, Ramsey sedation score 4 to 6, MASS (Motor Activity assessment Scale) 1 to 0 and GCS < 8 . Delirium Definition: Number of calendar days the patient is alive without delirium in the period from ICU admission to discharge. Delirium defined as above in secondary outcome 2. All assessments in a 24 hour period need to be negative for a patient to be assessed delirium-free).

5. Days alive without mechanical ventilation and days alive out of hospital (ICU) in a 90-day period

(Definition: Patient treated with mechanical ventilation either endotracheal intubated or tracheostomy, on controlled or spontaneous mode or patient treated with continuous non-invasive ventilation (NIV) for more than 1 hour. Number of days without a ventilator is registered every 24 hours; every new day at 6 AM is registered as one day. If a patient is re-intubated/or started NIV within 24 hours it will be registered as a full day of mechanical ventilation.

Definition: Number of days alive after discharge from the hospital (ICU), the day of discharge do not count, but from the next day at 6 AM).

6. Rate of cognitive impairment at 6 months after ICU discharge (only in Denmark)

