7.3 Statistical plan

The number of patients receiving haloperidol (totally and regularly, as needed and mixed dosing) will be presented as frequencies (% with 95% confidence intervals). Numeric data will be given as medians (interquartile range [IQR]). We will compare differences in baseline characteristics using non-parametric tests between patients who receive haloperidol and patients who do not receive haloperidol. To assess risk factors for the use of haloperidol, we will do multivariate analyses including patient characteristics (age, dialysis, shock and mechanical ventilation and delirium in the first 24 h of admission) and ICU characteristic (university hospital, guidelines for identifying and/or treating delirium and average staff-patient ratio). To assess if haloperidol is an independent predictor of 90-day mortality, we will do multivariate analysis including patient characteristics (age, dialysis, shock and mechanical ventilation and delirium in the first 24 h of admission) and time. We will do exploratory analyses on the interaction between delirium and use of haloperidol and the patient-relevant outcomes measure (mortality, days alive without mechanical ventilation and days alive and out for hospital). All statistical tests will be 2-tailed and $p < .05$ considered statistically significant.

8. Data Handling

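### Section 6.1 item 8 counts earlier delirium only if haloperidol was given, so the baseline risk factor is under-recorded and its comparison by haloperidol use may mislead

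*Protocol*

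**What the plan says.** Section 2.1 of the Protocol lists non-correctable risk factors for delirium "such as previous delirious episodes, age, dementia, smoking, alcohol and other drug abuse". No treatment condition is attached to the first of them.

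Section 6.1, item 8, collects this factor under the label "Risk factor status prior to hospital/ICU" and defines it: "Previous delirious episodes defined as: patients receiving one or more doses of haloperidol, AND described as delirious". A list of delirium criteria follows: screening scores, ICD-10 codes DF05, DF050 and DF058, behavioural signs including anxiety, and physical restraint.

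The two-part structure is that of the primary outcome in section 4.3.1: "Patients receiving one or more doses of haloperidol and are described as delirious". Secondary outcome 2 in section 4.3.2, the study's own delirium definition, begins "ICU documented CAM-ICU positive or ICDSC ≥ 4 points (0-8 points) or DOS >3 points (0-13/day points" and continues with codes, behavioural signs and restraint. It has no drug condition and does not mention anxiety.

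Section 7.3 then states: "We will compare differences in baseline characteristics using non-parametric tests between patients who receive haloperidol and patients who do not receive haloperidol".

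**The concern.** Item 8 is meant to measure whether a patient had been delirious before. As defined, it measures whether a patient had been delirious and had been given haloperidol. A patient whose earlier episode was untreated, or treated with another agent, is recorded as having had none. The protocol itself expects delirium to be managed without haloperidol: secondary outcome 1 counts delirious patients given other antipsychotics, and item 19 lists several other drugs. The anxiety term pulls the other way, because it admits patients whom secondary outcome 2 would not call delirious.

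Two things are at stake. The study's description of prior delirium will be too low. And because the study compares baseline characteristics by haloperidol use, a row that contains earlier haloperidol may differ between the groups even if true prior delirium does not. A reader would take this as prior delirium being associated with haloperidol use.

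**Working it through.** **Definitions side by side**

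| Place in Protocol | Concept | Haloperidol required? | Anxiety counts? |
|---|---|---|---|
| 2.1 | previous delirium as a risk factor | no | not mentioned |
| 4.3.1 | primary outcome | yes | no (uses outcome 2) |
| 4.3.2, outcome 2 | delirium | no | no |
| 6.1, item 8 | previous delirium | yes | yes |

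Item 8 matches neither the risk factor in 2.1 nor the delirium definition in 4.3.2. Nothing elsewhere in the Protocol qualifies it.

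**Where the variable is used.** The patient covariates listed for both multivariate models in 7.3 are "patient characteristics (age, dialysis, shock and mechanical ventilation and delirium in the first 24 h of admission". Delirium in the first 24 hours is a different variable, and previous episodes are not listed. No outcome in 4.3 uses item 8. The one planned use that the Protocol shows is the baseline comparison.

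**Under-recording.** Let π be the true share of patients with earlier delirium and f the fraction of those in whom haloperidol was given. Leaving the anxiety term aside:

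- recorded share = π × f
- missed share of earlier delirium = 1 − f

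The Protocol gives neither π nor f. For assumed f of 80%, 50% and 20%, the missed share is 20%, 50% and 80%.

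**Spurious difference.** With f_U among later haloperidol users and f_N among later non-users, and the same π in both groups:

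- odds ratio = [πf_U / (1 − πf_U)] ÷ [πf_N / (1 − πf_N)]

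For group sizes I take the 13% and 1000 patients of section 7.1. Its stated interval reproduces: 0.13 ± 1.96 × √(0.13 × 0.87 / 1000) = 0.13 ± 0.021, or 10.9% to 15.1%, against the stated 11%–15%. That gives 130 users and 870 non-users, if 13% applies to all patients; section 7.1 can also be read as 13% of delirious patients.

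Worked case, π = 10%, f_U = 60%, f_N = 40%: recorded shares are 6.0% and 4.0%, so the odds ratio is (0.06/0.94) ÷ (0.04/0.96) = 1.53.

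| f_U / f_N (assumed) | Recorded at π = 10% | Odds ratio at π = 10% | Odds ratio, π from 5% to 20% | Chance of p < 0.05 at π = 10% |
|---|---|---|---|---|
| 50% / 50% | 5.0% / 5.0% | 1.00 | 1.00 | no excess over the nominal level |
| 60% / 40% | 6.0% / 4.0% | 1.53 | 1.52–1.57 | 22% |
| 70% / 30% | 7.0% / 3.0% | 2.43 | 2.38–2.55 | 60% |
| 80% / 20% | 8.0% / 2.0% | 4.26 | 4.12–4.57 | 89% |

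The true odds ratio is 1.00 in every row. The last column is a two-sided normal-approximation calculation with 130 and 870 patients. With the haloperidol condition removed, the recorded share equals π in both groups and the odds ratio is 1.00 throughout.

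**The case against.** The strongest case on the other side is reach: the variable feeds one row of an unadjusted baseline comparison. The primary count, the secondary outcomes and the listed models do not depend on it. This stands and limits the weight of the point.

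Several stronger readings are tempting, but the documents do not support them.

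- *The comparison is circular.* Item 8 concerns status before hospital or ICU admission, whereas the groups in 7.3 are formed by haloperidol received during the study. These are different doses at different times. There is a built-in dependence on earlier haloperidol, not a tautology.
- *The variable simply measures prior haloperidol exposure.* It does not: a prior haloperidol user who meets none of the delirium criteria is coded as negative.
- *A spurious association is bound to appear.* That requires earlier haloperidol treatment to predict current use, and the Protocol has no data on this. With equal earlier treatment, only under-recording remains.
- *The 13% in section 7.1 means that 87% of earlier episodes are missed.* That figure is a current ICU rate from one department, not the treated share of past episodes. If it is read as 13% of all ICU patients and combined with the 16%–89% delirium incidence in section 2.1, the treated share among delirious patients runs from 0.13/0.89 = 15% to 0.13/0.16 = 81%. The missed share would then be 19% to 85%, and only if past episodes were treated like current ICU ones. No single figure can be defended.
- *The loss cannot be repaired.* Section 8.1 gives patient records as source data, so earlier delirium could in principle be abstracted again, at a cost.

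One might also argue that haloperidol serves as a marker for poorly documented past delirium. The Protocol does not say so, and item 8 already requires a documented score or code, or described signs. The eCRF is not shown, so how sites are actually asked is unknown; the Protocol definition is nonetheless the one stated.

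**Conclusion.** The point holds as an error of definition with limited reach. Item 8 contradicts the risk factor named in section 2.1 and the delirium definition in section 4.3.2. Followed as written, it records haloperidol-treated prior delirium and codes other earlier delirium as absent. This conclusion rests on the text alone.

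The size is not known. The missed share equals the fraction of earlier episodes managed without haloperidol, which the documents do not give. The spurious odds ratio in the baseline comparison ranges from 1.00 (equal earlier treatment) to about 1.5 (60% against 40%) and above 4 (80% against 20%). All of these rest on assumed treatment shares, equal true prior delirium in both groups and no contribution from the anxiety term. The primary outcome, the secondary outcomes and the listed multivariate models are unaffected.

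**What to change.** In section 6.1, item 8, delete the condition of at least one haloperidol dose, with the AND that joins it, and delete the anxiety term. Keep item 8's remaining delirium criteria and its own code list (DF05, DF050, DF058). Do not paste in secondary outcome 2 verbatim: its restriction to ICU documentation does not suit a history from before hospital or ICU admission, and its code list repeats DF05 where item 8 has DF058.

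Prior antipsychotic use is already recorded as a class in item 7 (N05A), which includes haloperidol (N05AD01). If earlier haloperidol is of interest in itself, flag it there. Item 7 as it stands cannot recover the earlier delirium that item 8 misses.

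The cost is one wording change in the Protocol and the matching eCRF text or guidance. Make it before data collection. Afterwards, patients coded negative could be separated into never delirious and delirious without haloperidol only by going back to the patient records.

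### Outcome 5 counts NIV only when continuous for more than 1 hour, but daily item 16 records any NIV that day with no duration

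*Protocol*

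**What the plan says.** Protocol section 4.3.2 names outcome 5 as "Days alive without mechanical ventilation and days alive out of hospital (ICU) in a 90-day period". Its definition has three parts that matter here:

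- **What counts.** Invasive ventilation by tube or tracheostomy counts. So does a "patient treated with continuous non-invasive ventilation (NIV) for more than 1 hour".
- **The day.** "Number of days without a ventilator is registered every 24 hours; every new day at 6 AM is registered as one day".
- **Restarts.** "If a patient is re-intubated/or started NIV within 24 hours it will be registered as a full day of mechanical ventilation".

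The data come from the daily collection in section 6.1. Item 16 asks, as yes/no, about invasive ventilation and about "use of non-invasive ventilation at any time during this day (y/n"). It has no field for duration, continuity, or start and stop times, and it does not say when the day begins.

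Outcome 4, which draws on the same set of daily items, uses a different day: "Number of calendar days the patient is alive without coma in the period from ICU admission to discharge".

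**The concern.** An outcome can be derived as defined only if the collected item separates the days that count from those that do not. Here the definition has a duration threshold and the item has none, so the item is wider than the definition. The error can go only one way: the item can add ventilated days that the definition excludes, and it cannot miss any that the definition includes.

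Days alive without mechanical ventilation is a secondary outcome. Section 7.3 also names it among the patient-relevant outcomes for the exploratory analyses of delirium and haloperidol use. About 50 ICUs are expected to abstract the data (section 3.1). With two criteria in one protocol, an abstractor could follow either.

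**Working it through.** The plan states no figure on this point, so there is none to reproduce. The check sets the outcome definition beside the daily item and classifies each kind of day under both.

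**Step 1: is there another source for NIV duration?** Baseline item 4 is a single yes/no. Items 20 to 22, at day 90, cover vital status, ICU discharge and hospital discharge. No other daily item concerns ventilation. Item 16 is therefore the only listed daily source.

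**Step 2: classify the days.**

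| Ventilation that day | 1-hour rule in outcome 5 | Item 16 | Agree? |
|---|---|---|---|
| (a) Any invasive ventilation | ventilated | yes | yes |
| (b) NIV only, continuous for more than 1 hour | ventilated | yes | yes |
| (c) NIV only, one session of 1 hour or less | not ventilated | yes | no |
| (d) NIV only, several short sessions, e.g. 3 × 40 minutes | not ventilated | yes | no |
| (e) None | not ventilated | no | yes |

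In (d) the sessions add up to 3 × 40 = 120 minutes, but none is continuous for more than 60 minutes. Rows (b), (c) and (d) all produce the same NIV answer and cannot be separated afterwards.

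**Step 3: direction and size.** A patient with k days of type (c) or (d) has k fewer days without ventilation than the definition gives. If a share p of patients have on average k such days, the cohort mean falls by p × k days. The protocol gives neither p nor k, so the product cannot be computed.

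**Step 4: does the list carry thresholds elsewhere?** Yes. Item 18 asks about opioid infusion lasting more than 2 consecutive hours. Item 17c gives duration limits for dexmedetomidine (more than 18 hours per day, or more than 4 hours continuously between 10 pm and 6 am). The list writes in a duration where one is intended, so its absence from item 16 is not just a matter of format.

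**Step 5: the restart sentence.** It registers NIV started within 24 hours as a full ventilated day, without a minimum duration and without naming the event from which the 24 hours run. If it overrides the 1-hour rule, some days in rows (c) and (d) count as ventilated and agree with item 16. If it does not, they remain in conflict.

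**Step 6: the day boundary.** Item 16 sets no clock boundary. If the record were kept in calendar days and outcome 5 read from it:

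- An episode from 23:00 to 05:00 touches 2 calendar days but 1 day counted from 6 AM (difference +1).
- An episode from 04:00 to 08:00 touches 1 calendar day but 2 days counted from 6 AM (difference −1).

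Midnight and 6 AM alternate, so the two counts for one continuous episode differ by at most 1, in either direction.

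**The case against.** **The form is not shown.** Section 6.1 is a list of variables, and section 8.1 says the electronic form is still to be programmed. A field instruction could carry the 1-hour rule from section 4.3.2. This stands as a limit: a reader might infer that outcome 5 cannot be derived at all, and the protocol does not show that. But the wording of item 16 points away from a threshold, and items 17c and 18 show that thresholds are written in where wanted. A form built from the list as it reads would have the fault.

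**The definition is itself unclear.** The restart sentence can be read as counting NIV of any length when it begins within 24 hours, so not every short session is clearly excluded. This also stands. It narrows the set of conflicting days, and it means that adding the 1-hour limit to item 16 alone could create a new mismatch: a short restart would be recorded as no but counted as a full day.

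**The day boundary.** A reader might infer that one daily record cannot serve both outcome 4 and outcome 5, or that the boundary adds to the downward error. Neither is supported. Item 16 names no boundary and so does not contradict 6 AM, nothing requires all daily items to share one boundary, and the effect can have either sign. What remains is that the day is undefined.

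**Effect on results.** A reader might infer a systematic difference between ICUs, or want to put a number on the error. The protocol says nothing about how often short NIV is used or how that varies by site. Numeric data are reported as medians with interquartile ranges (section 7.3), which a shift in a minority of patients may barely move.

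**Conclusion.** The NIV criteria in outcome 5 and item 16 contradict each other in the current text. If data are collected as item 16 reads, days whose only ventilation was short or non-continuous NIV are recorded as ventilated although the 1-hour rule excludes them. The outcome is then too low against its own definition by one day for each such day. An analysis plan cannot repair this, because the duration would never have been recorded.

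The conclusion assumes that the form follows the list, and that the restart sentence does not override the 1-hour rule for every such day. The total effect is unknown because the protocol gives no frequency. Days with invasive ventilation, the primary outcome and the sample size are unaffected. The undefined day boundary is a smaller matter of at most one day per episode, in either direction. This is an inexpensive correction to a secondary outcome, and it is best made before data collection.

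**What to change.** Use one NIV criterion in section 4.3.2 (outcome 5) and section 6.1 (item 16). Either:

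1. Write the outcome's criterion into item 16, so that it asks whether the patient had continuous NIV for more than 1 hour that day, in the way items 17c and 18 carry their thresholds; or
2. If the form is locked, redefine outcome 5 so that any NIV that day counts, and report it under that definition.

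In both cases, reconcile the restart sentence with the chosen criterion: say whether NIV started within 24 hours must also meet it, and from which event the 24 hours run.

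As a minor addition, state the clock boundary of the recorded day for the daily items and how it relates to the calendar days of outcome 4 and the 6 AM days of outcome 5.

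The cost is one form label or one sentence in the definition, plus a clarified restart sentence and a line on the day boundary. Under option 1, abstractors must check NIV duration in the chart, which is a small effort. After collection, the 1-hour rule could be applied only by going back to patient records.
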